7.3. Outcome Analysis

Data collected for this study will be used to assess the feasibility of refining the next generation G4 algorithm model.

8. Quality Control and Quality Assurance

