1.2. Study Rationale

The purpose of this study is to collect and analyze synchronized intra- and extravascular ECG data from subjects requiring PICC insertion using the G4 system and an external 12-lead ECG machine. This study will serve to determine the feasibility of using the comparison data collected to evaluate the correlation between intra- and extravascular ECG data, and to determine usability of the data in refining the next generation G4 system algorithm.

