1.3. Hypothesis

Data collected simultaneously from the G4 system and a 12-lead ECG machine during PICC insertion in adult subjects will be useful in evaluating the correlation between intra- and extravascular ECG recordings and refining the next generation G4 algorithm model.

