2.1. Primary Objective

The objective of this study is to collect and analyze synchronized intra- and extravascular ECG data from subjects receiving PICC insertion while using the G4 and a 12-lead ECG machine. The data will be analyzed to evaluate the correlation between intra- and extravascular ECG data.

Primary Endpoint

The primary endpoint is the successful collection of the following data: synchronized digital data collected from the G4 and ECG machines during the PICC insertion procedure, photographic images documenting ECG lead placement, and a chest x-ray of the inserted PICC (post procedure). A copy of the data will be submitted to the sponsor.

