3.2. Sample Size

A sample size of up to 30 adult subjects will be enrolled to obtain 20 evaluable subjects. Including a maximum of 10 subjects in whom the G4 system was used for tip navigation but the blue bull's eye was not achieved and 10 subjects where the blue bull's eye served as confirmation for tip placement. An adult subject per The Federal Food, Drug, and Cosmetic Act (FD&C Act) is persons 22 years of age and older at the time of treatment.^{vi} To be considered an evaluable subject, data must be collected for the duration of the PICC insertion procedure on both the G4 and the ECG machines, the post-insertion chest x-ray completed, and photographic documentation of the ECG lead placement captured. Non-evaluable subjects will be replaced to meet the target sample size.

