7.2.2. Feasibility Analysis Population

Non-evaluable subjects will be excluded from the feasibility analysis population. See Section 3.2 - Sample Size for definition of evaluable subject.

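### Collection success is 100% by construction in the feasibility population, and no correlation method or feasibility criterion is set in advance

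*Combined protocol and SAP*

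**What the plan says.** The primary objective in section 2.1 has two halves, collecting and analysing. On the second half it says: "The data will be analyzed to evaluate the correlation between intra- and extravascular ECG data". The endpoint under the same heading covers the first half only: "The primary endpoint is the successful collection of the following data", followed by synchronised G4 and 12-lead ECG data, photographs of lead placement and a post-procedure chest x-ray.

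Section 1.2 gives the aim as feasibility: "This study will serve to determine the feasibility of using the comparison data collected to evaluate the correlation between intra- and extravascular ECG data". Section 1.3 hypothesises that the data "will be useful in evaluating the correlation between intra- and extravascular ECG recordings and refining the next generation G4 algorithm model".

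On numbers, section 3.2 says: "A sample size of up to 30 adult subjects will be enrolled to obtain 20 evaluable subjects". It then defines an evaluable subject and provides for replacement of those who are not. Section 7.1 states that the sample size has no statistical justification.

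Section 7.2 names two populations. The safety set (7.2.1) holds everyone in whom G4/ECG recording was begun. For the feasibility set (7.2.2) the rule is: "Non-evaluable subjects will be excluded from the feasibility analysis population". Section 7.3 is a single sentence: "Data collected for this study will be used to assess the feasibility of refining the next generation G4 algorithm model".

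**The concern.** A feasibility study has to be able to show how often the procedure worked among those in whom it was tried. Here the only non-safety population is selected on the outcome that the primary endpoint measures. A site that obtained complete data from nearly everyone and a site that lost a third of its subjects would report the same figure.

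Two further gaps add to this. The correlation in the objective has no stated coefficient, lead pairing, unit of analysis or interval. Feasibility has no stated criterion. Both would then be chosen after the data are seen, which weakens any conclusion passed on to the algorithm work.

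**Working it through.** **1. Endpoint and evaluability side by side.**

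| Component | Primary endpoint (2.1) | Evaluable (3.2) |
|---|---|---|
| G4 and 12-lead data | required, synchronised | required on both machines, for the whole insertion |
| Photographs of lead placement | required | required |
| Post-insertion chest x-ray | required | required |

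The components are the same. Section 3.2 does not repeat the synchronisation condition, but section 4.4.1 makes clock setting mandatory before each subject. If 4.4.1 is followed, every evaluable subject meets the endpoint.

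**2. Success rate in the 7.2.2 population.** With m evaluable subjects the rate is m/m = 100% for any m. At m = 20 the exact lower 95% limit is 0.025^(1/20) = 0.832, giving 83.2% to 100%. That interval carries no information, because failures were removed before counting.

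**3. The plan's own figures.** These are 20 evaluable and up to 30 enrolled. The ratio is 20/30 = 66.7%, equivalent to allowing for one third non-evaluable, since 20/(1 − 1/3) = 30. The one third is back-calculated. The plan states no such assumption and no alpha, power or precision target, so there is no derivation to reproduce.

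**4. Rate with those started as denominator (illustration).** The Clopper-Pearson limits for x of n are the 0.025 quantile of Beta(x, n − x + 1) and the 0.975 quantile of Beta(x + 1, n − x).

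- 20 of 30: Beta(20, 11) and Beta(21, 10) give 66.7% (47.2% to 82.7%).
- 20 of 25: Beta(20, 6) and Beta(21, 5) give 80.0% (59.3% to 93.2%).

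Both would appear as 20/20 in the 7.2.2 population.

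**5. What the cap of 30 reveals.** If X is the number evaluable among 30, P(X ≥ 20) is 0.05, 0.29, 0.73 and 0.97 for assumed true rates of 50%, 60%, 70% and 80%. A shortfall below 20 would therefore be visible when the true rate is low. Quite different rates can still reach the target, and the plan ties no conclusion to either result.

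**6. Losses that are not collection failures.** Section 4.4 admits at most 10 subjects without a blue bull's eye and then ends participation for any further such subject, after recording has begun. These subjects sit in the 7.2.1 set. If 5 of 30 started were ended for this reason alone and 20 of the rest succeeded, the rate would be 20/(30 − 5) = 80%, not 67%. The two kinds of loss must be separated.

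**7. Photographs.** Section 3.2 requires them of every evaluable subject. Section 3.1 limits them to men while recruiting both sexes (its opening sentence mentions men only), and section 4.3 limits them to some consenting men. Read literally, no woman can be evaluable.

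**8. Correlation.** Nothing in section 7 mentions it. Section 4.4.1 allows the two clocks to differ by up to 1 second. At assumed heart rates of 60 to 100 per minute a beat lasts 60/60 = 1.0 s to 60/100 = 0.6 s, so the tolerance spans 1.0 to 1.7 beats. Clock time alone may not pair the same beat on both machines.

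**The case against.** The best defence is that this is an openly unpowered, single-centre feasibility study whose title describes data collection for model training. A collection endpoint fits the collecting half of the objective, and the missing correlation method is largely missing detail. The plan also never says that a collection rate will be reported in the 7.2.2 population. All of this is fair, and no power calculation is being asked for. But the endpoint in 2.1 is collection success, and 7.2.2 is the only population provided for feasibility. A reader following the plan would report the endpoint there.

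Four stronger readings are tempting and are not supported:

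- **That the plan yields no correlation result.** Section 2.1 commits to analysing the correlation. What is absent is the method.
- **That the plan cannot conclude against feasibility.** Sections 7.1 and 7.3 concern suitability for refining the algorithm, and 20 complete recordings could still prove unsuitable. Enrolment is capped at 30, and section 11.5 lists insufficiently complete data as a ground for termination. A negative judgement remains possible; it simply has no rule.
- **That section 7.3 addresses only data collection.** Its sentence is about refining the algorithm.
- **That heartbeats would be pooled across subjects as if independent.** The documents propose no such analysis, so no size can be attached to it.

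**Conclusion.** The concern holds in this form: the feasibility population is selected on the primary endpoint's own components, so collection success within it is 100% whatever the true rate. This rests on the wording of 2.1, 3.2 and 7.2.2, and on the clock setting in 4.4.1 being carried out. The 67% (47% to 83%) is an example that assumes all 30 permitted subjects are started and 20 succeed; it is not a forecast. The absence of a correlation method and of a feasibility criterion is a lesser gap in prespecification. None of this invalidates the data to be collected. It should be corrected before the first subject, because a criterion chosen afterwards would carry little weight.

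**What to change.** **Collection success (7.2.2 and 7.3).** Report the number of subjects with complete synchronised G4 and ECG recordings and a chest x-ray, divided by all subjects in the 7.2.1 set, with an exact 95% CI. Define completeness from 3.2 and 4.4, so that a recording that stops and is not resumed counts as a failure. Fix a minimum acceptable proportion before the first subject, and say whether the point estimate or the lower limit is judged against it. The choice matters: at 20 of 30 the interval is 82.7 − 47.2 = 35.5 percentage points wide.

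**Bull's-eye limit.** Subjects whose participation ended only because the limit of 10 in 4.4 had been reached should be taken out of the denominator, not counted as failures, and their number reported separately.

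**Photographs.** Reconcile the requirement in 3.2 with 3.1 and 4.3. The success measure above does not depend on photographs.

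**Correlation (7.3).** State that one coefficient is computed per subject, between the G4 intravascular signal and a named 12-lead channel, after a described alignment step. Summarise with the subject as the unit, overall and by bull's-eye group.

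**Cost.** Protocol and SAP wording and a little more analysis work, including the alignment. No new subjects or data are needed. The reported success figure may be below 100%.

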8.1. Sponsor

The Sponsor will confirm that the study meets GCP guidelines and all applicable regulatory requirements. The Sponsor will be allowed direct access to all study related sites, source documents, and reports for the purpose of monitoring and auditing by the Sponsor, and the inspection by regulatory agencies.

8.2. Investigators

Investigators will be responsible for implementing and maintaining quality assurance and quality control systems to ensure that the data is generated, recorded, and reported appropriately. Additionally, investigators are responsible for ensuring that the study is conducted according to this clinical study protocol. Investigators assume full responsibility for performance of the clinical study in accordance with this protocol, Good Clinical Practice, and all regulatory requirements applicable to the jurisdiction in which the study

sites are located. The Investigators will apply quality control measures to all stages of data handling to ensure reliability and accuracy and will confirm that the data is processed correctly.

9. Study Monitoring

9.1. General

Both the Investigators and the Sponsor of this study are responsible for taking all reasonable steps to ensure the proper conduct of the study regarding ethics, protocol compliance, integrity, and validity of the data recorded on the CRFs. At regular intervals during the study, the Investigator and Sponsor will communicate, through site visits, letters, or telephone calls to review study progress, compliance to protocol requirements, and any problems or issues.

Onsite Monitoring visits will be made periodically during the study to ensure that all aspects of the current, approved protocol are being followed. Original source documents will be reviewed for verification of selected data captured on the eCRF. Digital files will be reviewed and submitted to the sponsor.

The Investigator and site personnel will guarantee direct access to original source documents by Sponsor and their designees. In the event original medical records cannot be obtained for a subject who is seen by a non-study physician at a non-study institution, copies of original source documents must be made available for review. Copies of original source documents related to SAEs (from either the study site or a non-study institution, if applicable) must also be made available for submission to the Sponsor.

9.2. Protocol Deviations

A protocol deviation is any noncompliance with the clinical study protocol. As a result of deviations, corrective actions are to be developed by the site and implemented promptly. The study site is responsible for assuring that the protocol is followed, that subjects are included and assessed in accordance with the inclusion and exclusion procedures and that the subjects are seen and followed at designated times.

10. Institutional Review Board Review

10.1. Ethical Principals

This study will be conducted in accordance with GCP, as defined by the International Conference on Harmonization (ICH) guidelines, and all applicable regulations.

10.2. Institutional Review Board/Independent Ethics Committee

This study protocol will be reviewed and approved by an IRB prior to study implementation. A copy of the approval will be collected by the Sponsor.

10.3. Protocol Amendments

During the clinical trial, any amendment or modification to the protocol must be reviewed and approved by the IRB prior to implementation. The board or committee should also be informed of any event likely to affect the safety of subjects or the conduct of the study, in particular any change in safety and all updates to the IRB.

10.4. Progress Reports

As applicable, Investigator must send a report to the IRB, at least annually. A study closure report, including a summary of the trial's outcome will be reported at the end of the study.

11. Data Handling and Recording

11.1. Record Storage and Retention

The F.D.A. requires that essential documents be retained at the site for at least 2 years after the latter of the following two dates: The date on which the investigation is terminated or completed, or the date that the records are no longer required for purposes of supporting a premarket approval application, a notice of completion of a product development protocol, a humanitarian device exemption application, a premarket notification submission, or a request for De Novo classification.^v

11.2. Investigator Responsibilities

The Investigator will maintain all study documentation and institute measures to prevent accidental or premature destruction of any data and/or documents related to the study. After the formal discontinuation of the clinical study, the Investigator will retain the study documentation produced by the investigator for at least 2 years after the completion of the study (see 10.1). The Investigator will allow Sponsor and/or Sponsor's representatives to have access to the essential study documents.

11.3. Sponsor

The Sponsor will maintain all study documentation and institute measures to prevent accidental or premature destruction of any data and/or documents related to the study. The Sponsor will retain the study documentation permanently in accordance with Teleflex Record Control Global S.O.P. D0003064.

11.4. Data ownership

The Sponsor shall retain sole ownership of all data, results, reports, findings, and any other information collected during this study.

11.5. Early Termination of Study

This study may be terminated earlier than anticipated if, in the opinion of the investigator or the sponsor, there is sufficient reasonable cause. Written notification, documenting the reason for study termination, will be provided to the investigator or sponsor by the terminating party. Circumstances that may warrant termination include, but are not limited to:

- Insufficient adherence to protocol requirements
- Data that is not sufficiently complete and/or evaluable
- Plans to modify, suspend, or discontinue the study

If the study is terminated earlier than anticipated, the IRB will be informed promptly and provided the reason(s) for the early termination.

12. Confidentiality

All materials, information (oral or written) and unpublished documentation provided to the Investigators (or any company/institution acting on their behalf), inclusive of this protocol and the Subject CRFs, are exclusive property of the Sponsor and may not be given or disclosed, either in part or in whole, by the Investigator or by any person under his/her authority to any third party without written approval from the Sponsor. The submission of this protocol and other necessary documentation to the IRB is expressly permitted. The IRB members have the same obligation of confidentiality.

The Investigator will consider all information, results, discoveries, records accumulated, acquired, or deduced in the course of the study, other than that information to be disclosed by law, as confidential and will not disclose any such results, discoveries, records to any third party without written notification to the Sponsor.

13. Publication Policy

The Sponsor and Investigator agree that it is not anticipated that any publication will result from the Study, however each party retains the right to publish the Study Data and results of the Study in a manner compliant with the Protocol and the International Committee of Medical Journal Editors Recommendations for the Conduct, Reporting, Editing and Publication of Scholarly Work in Medical Journals in effect as of the date of initiation of the Study.

References

ⁱ Santolim TQ, Baptista AM, Giovani AMM, Zumárraga JP, Camargo OP. Peripherally inserted central catheters in orthopedic patients : Experience from 1023 procedures. *Acta Ortop Bras.* 2018;26(3):206-210. doi:10.1590/1413-785220182603189368

